7.3 Disposition of Subjects

Subjects' study completion data, including reasons for premature termination, will be provided in listings and also summarized. Summaries of the reasons for premature termination will be presented separately for the healing period and for the maintenance of healed EE period.

A summary of screening failures and listings of inclusion/exclusion criteria responses will be provided.

Significant protocol deviations captured on the electronic Case Report Form will be summarized.

7.4 Demographic and Baseline Characteristics

Demographic variables will be summarized for the FAS-H and the FAS-M. For continuous variables (age, weight, height and body mass index [BMI]), summary statistics will be generated. The number and percentage of subjects in each category will be presented (eg, gender, race). BMI (in kg/m²) will be calculated using the subject's baseline height and weight measurement and summarized.

7.5 Medical History and Concurrent Medical Conditions

Medical history and concurrent medical conditions will be coded using MedDRA. Medical history and concurrent medical conditions will be presented in a data listing.

7.6 Medication History and Concomitant Medications

All medication history and concomitant medications will be coded by therapeutic classification, subclassification, and medication using the World Health Organization Drug Dictionary (WHO Drug). A concomitant medication is defined as a medication that is ongoing as of Study Day 1, ends on or after Study Day 1, or starts on or after Study Day 1 and no more than 1 day after the last dose of study drug. Medication history and concomitant medications will be presented in a data listing.

7.7 Study Drug Exposure and Compliance

Overall study drug compliance (%) will be determined as (total count of capsules taken) / total number of days on study drug × 100%, separately for the healing period and for the maintenance period.

For the healing period, the total number of days on study drug (exposure) will be calculated as date of last dose of study drug - date of first dose of study drug + 1, assuming there is no gap in the dosing. If the last dose date is missing, then the duration of the treatment period will be imputed as 70 days or the day before first dose date in maintenance period, whichever is earlier.

For the maintenance period, the total number of days on study drug (exposure) will be calculated as date of last dose of maintenance study drug - date of first dose of maintenance study drug + 1, assuming there is no gap in the dosing. Any gaps in dosing will be ignored when calculating the total. If the last dose date of the maintenance period is missing, then the duration of the maintenance period will be imputed as 189 days.

Subjects with unreturned study drug will be assumed to have taken 1 capsule of study drug for each day of exposure for the calculation of overall compliance. Subjects with overall compliance $\geq 100\%$ will be set to 100% in the analysis.

In addition, diary compliance will be determined as the percentage of days during treatment with diary entries.

Diary Compliance =

(Number of days with two diary entries collected during treatment period) / (Number of days with two diary entries expected during treatment period) $\times 100\%$

Exposure and compliance data will be presented in a data listing.

7.8 Efficacy Analysis

The efficacy endpoints will be summarized using the FAS-H for the healing period and using the FAS-M for the maintenance period.

7.8.1 Primary Efficacy Endpoint

The primary efficacy variable will be the percentage of subjects who have complete healing of EE over 8 weeks as assessed by endoscopy. Subjects who do not have endoscopically documented healing and who prematurely discontinue will be considered as not healed. The primary endpoint will be presented in a data listing and summarized for the Healing period for the FAS-H.

7.8.2 Secondary Efficacy Endpoints

The secondary efficacy variable will be the percentage of subjects who maintained complete healing of EE over 6 months as assessed by endoscopy. Subjects who do not have endoscopically documented maintenance of healing and who prematurely discontinue will be considered to have relapsed. The secondary endpoint will be presented in a data listing and summarized for the Maintenance period for the FAS-M.

If a subject's final endoscopy was performed prior to the Month 6 Visit and indicated recurrence of EE, the subject will be considered to have recurrence of EE at the Month 6 Visit.

7.8.3 Additional Efficacy Endpoints

All additional efficacy variables will only be presented in data listings, no summary tables will be produced. The following are the additional efficacy variables to be listed:

The severity of GERD symptoms at Weeks 4 and 8 as assessed by the investigator during the Healing Period.

The percentage of days with neither daytime nor nighttime heartburn and the percentage of days without rescue medication use over the 8 weeks of the Healing Period and over the 6 months of the Maintenance Period as assessed by the daily diary.

- The severity of daytime and nighttime heartburn over the 8 weeks of the Healing Period and over the 6 months of the Maintenance Period as assessed by daily Diary.
- The severity of nighttime heartburn over the 8 weeks of the Healing Period and over the 6 months of the Maintenance Period as assessed by daily Diary.
- The severity of daytime heartburn over the 8 weeks of the Healing Period and over the 6 months of the Maintenance Period as assessed by daily Diary.

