13.1.3 Efficacy Analysis

The primary efficacy variable will be the percentage of subjects who have complete healing of EE over 8 weeks as assessed by endoscopy. The treatment difference of healing rate between dexlansoprazole and lansoprazole will be calculated and the lower bound of 95% confidence interval will be compared with -10%. Noninferiority to lansoprazole will be declared if the lower bound is greater than -10%. Subjects who do not have endoscopically documented healing and who prematurely discontinue will be considered as not healed.

The secondary efficacy variable will be the percentage of subjects who maintained complete healing of EE over 6 months as assessed by endoscopy. A comparison between dexlansoprazole capsules and placebo will be made using Cochran-Mantel-Haenszel (CMH) test using

stratification factor of baseline grade. Subjects who do not have endoscopically documented maintenance of healing and who prematurely discontinue will be considered to have relapsed.

An additional efficacy variable will be the severity of GERD symptoms at Weeks 4 and 8 as assessed by the investigator during the Healing Period. The severity of GERD will be compared between dexlansoprazole and lansoprazole capsules using a CMH test for ordered responses with baseline severity as the stratum. The number of subjects at each severity level for each GERD symptom at Months 1, 3, 6 will be also summarized by treatment group and baseline severity. At each visit, the severity will be compared between treatment groups using a CMH test for ordered responses (row mean score statistic with table scores of 0, 1, 2, 3, and 4) with baseline severity as the strata.

The percentage of days with neither daytime nor nighttime heartburn and the percentage of days without rescue medication use over the 8 weeks of the Healing Period and over the 6 months of the Maintenance Period as assessed by the daily diary will be summarized by treatment groups. Comparisons between treatment groups will be made using Wilcoxon rank-sum tests.

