For the purpose of the diary compliance calculation and derivation of diary-based endpoints, the last day of study drug in each period will not be included since the subject will not be expected to have completed the diary entries for that day by the Week 8 or month 6 Final Visit. Therefore, summaries for the healing period weeks of treatment will include Study Day 1 through Study Day 70 or the day before the last dose of healing period study drug, or the day before the first dose of maintenance study drug, whichever occurs first; summaries for the Maintenance period will include the day of the first dose of maintenance study drug through maintenance Study Day 180 or the day before the last dose of maintenance study drug, whichever occurs first.

Table 7.b Visit Windows for Maintenance Period

Visit	Scheduled Day	Safety Labs and Vital Signs	Serum Gastrin	ECG	Endoscopy	GERD Symptoms Investigator Assessment
Maintenance Baseline	-1M	≤1M	≤1M	≤1M	≤1M	≤1M
Month 1	30M	2M-60M	2M-60M	NA	2M-60M	2M-60M
Month 3	90M	61M-135M	61M-135M	NA	61M-135M	61M-135M
Month 6	180M	136M-210M	136M-210M	2M-210M	136M-210M	136M-210M

Note: Safety laboratory (including gastrin), vital signs, and ECG data obtained more than 7 days after the last day of study drug of Maintenance period and efficacy data obtained more than 7 days after the last day of study drug of Maintenance period will not be included in the analyses.
 M=Maintenance Period.

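### SAP 7.8.3 confines all additional efficacy endpoints to listings, although Protocol 13.1.3 prespecifies between-group summaries and tests for them

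*SAP*

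**What the plan says.** **SAP.** Section 5.3 names six additional endpoints: heartburn-free days and rescue-free days (as percentages, each in the Healing and Maintenance Periods), and investigator-rated GERD severity at Weeks 4 and 8 and at Months 1, 3 and 6. Section 7.8.3 then rules: "All additional efficacy variables will only be presented in data listings, no summary tables will be produced". The parent section, 7.8, says in general terms: "The efficacy endpoints will be summarized using the FAS-H for the healing period and using the FAS-M for the maintenance period".

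**Protocol 13.1.3.** On GERD severity in healing: "The severity of GERD will be compared between dexlansoprazole and lansoprazole capsules using a CMH test for ordered responses", stratified by baseline severity. On maintenance: "The number of subjects at each severity level for each GERD symptom at Months 1, 3, 6 will be also summarized by treatment group", split further by how severe the symptom was at baseline. A CMH row-mean-score test with scores 0 to 4 follows for each visit. The diary percentages are to be summarized by treatment group in both periods, and "Comparisons between treatment groups will be made using Wilcoxon rank-sum tests".

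**Primary and secondary endpoints.** Protocol 13.1.3 says of the healing-rate difference that "the lower bound of 95% confidence interval will be compared with -10" percent. For maintenance it says: "A comparison between dexlansoprazole capsules and placebo will be made using Cochran-Mantel-Haenszel (CMH) test using" baseline grade as the stratification factor. SAP 7.8.1 and 7.8.2 say only that these endpoints are listed and summarized.

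**The concern.** Protocol 13.1 leaves it to the SAP to supply the detail of the methodology, and requires the SAP to be final before unblinding. Here the SAP does not add detail to the protocol's plan for the additional endpoints; it removes that plan. An analyst who follows the SAP produces no group summary and no comparison for any of them. An analyst who follows the protocol produces both.

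If the conflict is still open at unblinding, the decision whether to run these comparisons can be made with the results in view. A reader of the report could not then tell a planned omission from a selective one. What is at stake is the credibility of the symptom and rescue-medication results, not the healing or maintenance conclusions.

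**Working it through.** **1. The six endpoints side by side**

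| Additional endpoint (SAP 5.3) | Protocol 13.1.3 | SAP 7.8.3 |
|---|---|---|
| Heartburn-free days, healing | Summary by group, Wilcoxon | Listing only |
| Heartburn-free days, maintenance | Summary by group, Wilcoxon | Listing only |
| Rescue-free days, healing | Summary by group, Wilcoxon | Listing only |
| Rescue-free days, maintenance | Summary by group, Wilcoxon | Listing only |
| GERD severity, Weeks 4 and 8 | CMH, ordered responses | Listing only |
| GERD severity, Months 1, 3, 6 | Summary by group, CMH, ordered responses | Listing only (covered by the opening sentence, but missing from the list beneath it) |

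Planned comparisons by endpoint: protocol 6 of 6, SAP 0 of 6.

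**2. Number of tests.** Wilcoxon: 2 percentages × 2 periods = 4. CMH: 2 + 3 = 5 visits. Protocol 9.1.6 grades five symptoms separately and the documents define no composite GERD score. If each symptom is tested at each visit, that is 5 × 5 = 25 CMH tests and 25 + 4 = 29 in all. The protocol does not state outright that the test is per symptom, so 29 rests on that assumption. The firm figure is six of six endpoints.

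**3. Is the departure explained?** No section gives a reason. SAP 7.13 records no changes, but its heading concerns changes in the SAP, so little should be built on it.

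**4. Does this touch the powered comparisons?** The stated maintenance power (SAP 6.0: 14% vs 66%, 33% dropout, 150 per arm, 2-sided 0.05, at least 99%) was reproduced by a two-proportion test.

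- With 100 completers per arm, power exceeds 99.99%.
- With every dropout counted as relapsed, the rates are 0.67 × 0.14 = 0.094 and 0.67 × 0.66 = 0.442, with mean 0.268.
- z = [0.348 − 1.96 × √(2 × 0.268 × 0.732 / 150)] / √[(0.094 × 0.906 + 0.442 × 0.558) / 150] = (0.348 − 0.100) / 0.047 ≈ 5.3, so power again exceeds 99.99%.

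For healing (85% in both arms, margin 10 points, 1-sided 0.025, 80% power): n = 2 × 0.85 × 0.15 × (1.960 + 0.842)² / 0.10², about 200.2, hence 201 evaluable per arm. Then 201 / 0.90 = 223.3, hence 224 against the 225 planned.

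Both stated figures hold, and nothing in this point changes them.

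**The case against.** The best defence is that the reduction may be deliberate. These endpoints lie outside the primary and secondary objectives and the sample size. Protocol 13.1 delegates methodology to the SAP and foresees a blinded review of whether the planned methods are appropriate. A pre-unblinding decision to report less on additional endpoints is legitimate, and no passage says that it must take the form of a protocol amendment. All of that stands. It does not remove the conflict, because the SAP neither declares the reduction nor gives a reason, and Protocol 13.1.3 still plans the tests.

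A reader might infer three stronger things that the documents do not support.

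- **That the SAP flatly contradicts itself.** SAP 7.1.1 says that "summaries for the healing period weeks of treatment will include Study Day 1 through Study Day 70", subject to earlier cut-offs. The purpose stated there is diary compliance and the derivation of diary endpoints. It fixes which days enter each subject's value, which a listing also needs, and promises no group tables. The general sentence in SAP 7.8 assigns analysis sets, and the more specific 7.8.3 can be read as overriding it. It sits awkwardly with 7.8.3 but is not decisive.
- **That the maintenance comparison has no prespecified test.** No SAP section names one, but the protocol's synopsis and Section 13.1.3 both give the CMH test stratified by baseline grade. SAP 4.2 and 6.0 supply the objective and the significance level, and the SAP offers no competing method.
- **That the noninferiority rule is lost.** SAP 7.8.1 is silent on the interval, but SAP 6.0 keeps the −10% rule and the protocol specifies the 95% interval.

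The last two are missing detail that the protocol fills.

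**Conclusion.** The conflict between SAP 7.8.3 and Protocol 13.1.3 is real and cannot be read away. Followed as written, the SAP drops the planned between-group comparison for six of six additional endpoints without explanation. It should be settled before unblinding.

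Its weight is moderate. It concerns additional endpoints only, the protocol still holds the prespecified analyses, and it causes no bias, loss of power or change in the primary or secondary conclusion. It is not a defect on which the validity of the trial turns. The silence of SAP 7.8.1 and 7.8.2 on inference is a drafting gap and does not raise that weight. The absence of Months 1, 3 and 6 from the 7.8.3 list is editorial.

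The conclusion assumes that Protocol 13.1.3 and the SAP are both in force as shown, and that no separate document records the change.

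**What to change.** Before unblinding:

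1. In SAP 7.8.3, replace the listings-only sentence with the protocol's analyses: by-treatment summaries and Wilcoxon rank-sum tests for both diary percentages in both periods, and row-mean-score CMH tests stratified by baseline severity for GERD severity at Weeks 4 and 8 and Months 1, 3 and 6, with the severity summary at the three maintenance visits. Add the maintenance GERD item to the list, and state whether each symptom is tested separately.
2. If the reduction is intended, declare and justify it in the SAP, reconcile it with Protocol 13.1.3, and word SAP 7.8 so that the exception is visible.
3. As housekeeping, carry the protocol's methods into the SAP. In 7.8.2, give the CMH test at 2-sided 0.05, stratified by the pre-healing grade (A/B vs C/D). The words pre-healing matter: SAP 7.1.1 sets the Maintenance Period baseline at Week 8, when every entrant is healed, so that definition taken literally would leave a single stratum. In 7.8.1, give the healing-rate difference (dexlansoprazole minus lansoprazole) in FAS-H with its 2-sided 95% confidence interval, compared with −10%.

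The cost is SAP text and routine tables. No new data, visits or subjects are needed.

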7.9 Pharmacokinetic/Pharmacodynamic Analysis

Not applicable.

7.10 Other Outcomes

Not Applicable.

7.11 Safety Analysis

All safety analyses will be performed using the Safety Analysis Set-H for the Healing Period, and using the Safety Analysis Set-M for the maintenance period. Results will be summarized by treatment group.

7.11.1 Adverse Events

All AEs will be coded using the Medical Dictionary for Regulatory Activities (MedDRA).

A Treatment Emergent Adverse Event (TEAE) will be defined as an AE that starts or worsens on or after Study Day 1, and no more than 30 days after the last dose of study drug. All TEAEs will be listed by subject number and MedDRA coding. A listing of all unique coded terms will also be provided.

The following summaries of TEAEs will be presented separately:

- TEAEs for subjects who enter into the Healing Period, occurring during the 8 week healing period (ie, TEAE starts or worsens on or after the first dose of healing phase study drug and no more than 30 days after the last dose if a subject does not receive any maintenance study drug or before the first dose of maintenance study drug) will be summarized by treatment group using the Safety Analysis Set-H.
- TEAEs for subjects who enter into Maintenance period, occurring during the 6 months maintenance treatment period (ie, TEAE starts or worsens on or after the first dose of maintenance study drug and before 30 days after last dose of maintenance) will be summarized by treatment group using the Safety Analysis Set-M.

The number and percentage of subjects with TEAEs will be summarized in several different tables:

- All AEs by system organ class (SOC), high level term (HLT), and preferred term (PT).
- Treatment-related AEs (TRAEs) by SOC, HLT, and PT.
- Most frequent AEs by SOC and PT (sorted by frequency of PT occurring in $\geq 5\%$ of subjects).
- Most frequent TRAEs by SOC and PT (sorted by frequency of PT occurring in $\geq 2\%$ of subjects).
- Severity of all AEs by SOC and PT (mild, moderate, or severe).
- Severity of TRAEs by SOC and PT (mild, moderate, or severe).
- Relationship to study drug for all AEs by SOC and PT (not related, related).

A subject with 2 or more AEs within the same level of the MedDRA term will be counted only once in that level using the most extreme incident (most severe for the severity tables and related for the relationship to study drug tables).

Additionally, treatment-emergent serious AEs, deaths and TEAEs resulting in premature discontinuation from study drug will be listed and summarized by SOC and PT. The most frequent treatment-emergent non-serious AEs will also be summarized by SOC and PT.

A pre-treatment event will be defined as an AE that starts before Study Day 1. A list of pre-treatment AEs by subject number and MedDRA coding will be presented separately. Pre-treatment AEs will be summarized by SOC, HLT and PT.

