2.0 STUDY SUMMARY

Name of Sponsor(s): Takeda Development Center Asia, Pte. Ltd.		Compound: Dexlansoprazole	
Title of Protocol: A Phase 3 Study to Evaluate the Efficacy and Safety of Dexlansoprazole (60 mg QD) and an Active Comparator, Lansoprazole (30 mg QD) on Healing of Erosive Esophagitis, and Maintenance of Healing in Subjects With Healed Erosive Esophagitis With Dexlansoprazole (30 mg QD) and Placebo		IND No.: Not applicable	EudraCT No.: Not applicable
Study Number: TAK-390MR_301		Phase: 3b	
Study Design: This is a phase 3, randomized, double-blind, multicenter, active-controlled, 2-arm study with an initial 8-week Healing Period, followed by a randomized, double-blind, placebo-controlled 6-month Maintenance Period. The study is designed to evaluate healing of erosive esophagitis (EE), maintenance of healed EE and the effect of therapy on relieving gastroesophageal reflux disease (GERD) related symptoms			
Primary Objectives: The primary objective is to determine the efficacy of dexlansoprazole capsules (60 mg once daily [QD]) compared with lansoprazole capsules (30 mg QD) in healing EE over 8 weeks of treatment in Chinese subjects with endoscopically-proven EE.			
Secondary Objectives: The secondary objective is to confirm the efficacy and safety of dexlansoprazole capsules (30 mg QD) compared with placebo in the maintenance of healing of EE over 6 months of treatment in Chinese subjects with healed EE.			
Subject Population: Subjects 18 years or older, inclusive, with EE.			
Number of Subjects: Estimated total: approximately 450 EE Healing (8 Weeks): 
 Approximately 225 subjects/ dexlansoprazole 60 mg capsules. Approximately 225 subjects/ lansoprazole 30 mg capsules. Maintenance (6 Months): 
 Approximately 150 subjects/dexlansoprazole 30 mg capsules. Approximately 150 subjects/placebo. 		Number of Sites: Estimated total: 25 sites in China	
Dose Level(s): Healing Period: Dexlansoprazole 60 mg capsules QD Lansoprazole 30 mg capsules QD Maintenance Period: Dexlansoprazole 30 mg capsules QD Placebo QD		Route of Administration: Oral	
Duration of Treatment: 32 Weeks		Period of Evaluation: 39 Weeks	

Main Criteria for Inclusion:

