At the Week 8 Visit, all subjects will undergo a physical examination including vital signs, laboratory evaluations, fasting serum gastrin, serum and urine pregnancy test (all women of childbearing potential), ECG and an endoscopy. In addition, study drug will be collected, a review of concomitant medication use will be performed, and an assessment of AEs will be conducted. If the subject's EE has healed completely as determined by endoscopy, the subject will have completed the Healing Period of the study, and will continue in the Maintenance Period. If the subject's EE has not completely healed after 8 weeks of treatment, all Final Visit procedures will be performed and the subject will not be eligible to continue into the Maintenance Period.

For subjects who prematurely discontinue during the Healing Period, efforts should be made to perform all procedures scheduled for the Week 8 / Early Termination Visit no later than 5 days after the last dose of study drug.

At the start of the 6-Month Maintenance Period, subjects with healed EE will be randomized in a 1:1 ratio to one of the following 2 groups; the randomization will be stratified by baseline endoscopic findings (grades A/B or C/D).

- Group I: dexlansoprazole capsules (30 mg QD)
- Group II: placebo (QD)

During the 6-month Maintenance Period, study drug will be self-administered orally, QD in the morning before breakfast. Subjects will continue to document the presence and maximum severity of daytime and nighttime heartburn symptoms using a diary. Subjects will also record the use of rescue medication. Subject visits will be conducted at Months 1, 3 and 6, of the Maintenance Period to collect and/or dispense study drug, assess GERD symptoms, review concomitant medication use, and assess AEs. Endoscopies will be performed at Months 1 and 6/Final Visit to evaluate maintenance of healed EE. Subjects with endoscopic evidence of relapsed EE will be discontinued from the study.

At the Month 1 Visit, the subject will undergo a physical examination including vital signs, laboratory evaluations, endoscopy, and urine pregnancy test (all women of childbearing potential).

[figure not shown]

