13.1.4 Safety Analysis

Safety will be assessed by summarizing the incidence of AEs, clinical laboratory values, gastrin levels, ECG, and vital signs.

Summary of AEs, ECG results, clinical laboratory values, gastrin levels, and vital signs will be provided separately for the Healing Period and for the Maintenance Period. For the Healing Period, baseline values will be the last available assessment before the first dose of study drug. The baseline values for the Maintenance Period will be the assessment performed at the Week 8 visit of the Healing Period.

All AEs will be coded using MedDRA. Treatment-emergent adverse events (TEAE) will be summarized using preferred term and primary system organ class overall, by severity, and by relationship to study drug for each treatment group. Separate summaries will also be generated for treatment-related adverse events (TRAEs) overall and by severity. AEs that were reported more than once by a subject during the same period will be counted only once for that subject and period at the maximum severity.

Other safety assessments (ECG results, clinical laboratory values, gastrin levels, and vital signs) will be summarized by double-blind treatment group at all visits assessed using descriptive statistics. Values outside the reference ranges and markedly abnormal laboratory values will be flagged and tabulated.

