6.0 DETERMINATION OF SAMPLE SIZE

A total of 450 subjects with EE documented during Screening are planned to be enrolled into this study. Approximately 300 subjects are expected to enter the Maintenance treatment period.

Assuming a 10% dropout rate during the Healing Period and an 85% healing rate at Week 8 for both lansoprazole and dexlansoprazole, 225 subjects per arm will provide at least 80% power at the 1-sided 0.025 level of significance to meet the noninferiority criteria between lansoprazole and dexlansoprazole. Noninferiority to lansoprazole will be declared if the lower bound of the confidence interval for the difference in healing rates is greater than -10%.

The fixed noninferiority margin of -10% is based on a double-blind, parallel-group, comparative study that evaluated EE healing rates after an 8-week treatment period with lansoprazole 30 mg QD or placebo. In this study, the difference in response rate between the lansoprazole 30 mg dose group and the placebo group was 40.4%; the lower limit of the 2-sided 95% confidence interval was 25.9%. Hence, even with a conservative assumption of this lower bound as the treatment effect of lansoprazole 30 mg, a -10% noninferiority margin would assure that dexlansoprazole 30 mg retains more than 60% of the treatment effect of lansoprazole 30 mg.

Assuming a 33% dropout rate during the Maintenance Period and that maintenance rates are 14% and 66% for placebo and dexlansoprazole 30 mg, respectively, 150 subjects per arm will have at least 99% power at the 2-sided 0.05 level of significance to detect a difference between the treatment groups.

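### Crude Maintenance TEAE percentages may overstate dexlansoprazole relative to placebo, because exit on detected relapse shortens placebo time at risk and no exposure-adjusted rate is planned

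*SAP*

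**What the plan says.** **Exit rule.** Protocol 6.1: "Subjects with endoscopic evidence of relapsed EE will be discontinued from the study". Protocol 9.1.16, the notes to Protocol Appendix A and SAP 4.3 agree. Scheduled Maintenance endoscopies are at Months 1 and 6 only. An endoscopy at Month 3 or an unscheduled visit is optional and prompted by symptoms (Protocol 6.1, Appendix A).

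**Expected failure.** SAP 6.0 and Protocol 13.2 assume that "maintenance rates are 14% and 66% for placebo and dexlansoprazole 30 mg, respectively", so 86% and 34% are expected to fail.

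**Adverse-event summary.** SAP 7.11.1, for Safety Set-M by treatment group: "The number and percentage of subjects with TEAEs will be summarized in several different tables". Protocol 13.1.4 plans the same kind of summary: "Treatment-emergent adverse events (TEAE) will be summarized using preferred term and primary system organ class overall". Neither document plans a person-time rate or a time-to-first-event analysis. SAP 7.7 derives days on drug, but exposure is only listed.

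**Windows.** SAP 7.11.1 counts a Maintenance TEAE until 30 days after the last dose. Under Protocol 10.2.1.1, routine collection stops at the Final or Early Termination Visit, followed by one phone call 5 to 10 days after the last dose.

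**Objective.** The Study Summary reads: "The secondary objective is to confirm the efficacy and safety of dexlansoprazole capsules (30 mg QD) compared with placebo". Protocol 5.1.2 and SAP 4.2 state the secondary objective as efficacy only.

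**The concern.** Efficacy itself determines how long a subject is watched. If placebo subjects relapse more often and some leave at Month 1, they have fewer days on which an adverse event can be recorded. A crude percentage then mixes risk with time at risk. A drug with exactly the placebo event rate will tend to show a higher percentage, and a true difference in either direction is distorted by the same mechanism.

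The tables are descriptive, but they are laid out by arm and will be read across. The cut-offs of 5% (all events) and 2% (treatment-related events) in the most-frequent tables of SAP 7.11.1 use the same percentages. Because exposure is only listed, a reader of the tables would not see that follow-up differs.

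**Working it through.** **1. The plan's own figure.** SAP 6.0 claims "at least 99% power at the 2-sided 0.05 level of significance to detect a difference between the treatment groups", with 150 per arm and 33% dropout. Evaluable per arm: 150 × 0.67 = 100.5, taken as 100. Standard error under the null, pooled p = 0.40: √(2 × 0.40 × 0.60/100) = 0.0693. Under the alternative: √((0.14 × 0.86 + 0.66 × 0.34)/100) = 0.0587. Then z = (0.52 − 1.96 × 0.0693)/0.0587 = 6.5, so power exceeds 0.9999 and the claim reproduces. If dropouts count as relapse, the rates are 0.14 × 0.67 = 9.4% and 0.66 × 0.67 = 44.2%, and power with 150 per arm still exceeds 0.9999. The documents give no expected follow-up by arm.

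**2. Mean follow-up to Day 180, without dropout.** Inputs: 14% and 66% remaining healed (SAP 6.0); Days 30, 90 and 180 (SAP Table 7.b). Assumption not in the documents: constant relapse hazard, so S(t) = m^(t/180) with m = 0.14 or 0.66.

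- S(30) = 0.7206 placebo, 0.9331 dexlansoprazole. S(90) = 0.3742 and 0.8124.
- Found at Months 1 and 6 only: 30(1 − S(30)) + 180 S(30).
- Found at Months 1, 3 and 6: 30(1 − S(30)) + 90(S(30) − S(90)) + 180 S(90).
- Immediate exit: (1 − m)/h, with h = −ln(m)/180.

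| Relapse detection | Placebo, days | Dexlansoprazole, days | Ratio | Ratio with 30 days added to each arm |
|---|---|---|---|---|
| Months 1 and 6 | 138.1 | 170.0 | 0.81 | 0.84 |
| Months 1, 3 and 6 | 106.9 | 159.1 | 0.67 | 0.72 |
| Immediate exit | 78.7 | 147.3 | 0.53 | 0.61 |

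The last column treats the 30-day window as fully observed, which the 5-to-10-day call does not achieve.

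**3. Without the constant-hazard assumption.** Let a share f of failures be found at Day 30 and the rest at Day 180. Mean follow-up is 180 − 150 × 0.86f on placebo and 180 − 150 × 0.34f on dexlansoprazole.

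- f = 0: 180 and 180, ratio 1.00
- f = 0.4: 128.4 and 159.6, ratio 0.80
- f = 0.8: 76.8 and 139.2, ratio 0.55
- f = 1: 51 and 129, ratio 0.40

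**4. Crude TEAE percentage with the same event hazard in both arms.** Assumptions: 30% risk over 180 days, λ = −ln(0.70)/180 = 0.00198 per day; the planned 33% dropout as an independent constant hazard, d = −ln(0.67)/180 = 0.00222; collection to 7.5 days after exit, the middle of the call window. For a relapse exit at day R,

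P(R) = 1 − e^(−7.5λ) [ d/(d+λ) × (1 − e^(−(d+λ)R)) + e^(−(d+λ)R) ].

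This gives P(30) = 0.0698 and P(180) = 0.2612. For Months 1 and 6:

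- placebo: 0.2794 × 0.0698 + 0.7206 × 0.2612 = 20.8%
- dexlansoprazole: 0.0669 × 0.0698 + 0.9331 × 0.2612 = 24.8%

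| Relapse detection | Placebo | Dexlansoprazole | Excess, points | Chance of nominal p < 0.05, 150 per arm |
|---|---|---|---|---|
| Months 1 and 6 | 20.8% | 24.8% | 4.1 | 0.13 |
| Months 1, 3 and 6 | 17.3% | 23.6% | 6.3 | 0.27 |
| Immediate exit | 13.5% | 22.2% | 8.6 | 0.50 |

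Excesses are from unrounded values. At a 50% risk the chances are 0.21, 0.44 and 0.74. If half the event hazard falls in the first 30 days (30% risk), the excess drops to about 2 to 6 points and the chances to 0.07 to 0.22. Under a constant event hazard, an event rate per person-time has an expected ratio of 1.0 in every row.

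**The case against.** **Relapse timing is unknown.** A subject leaves when endoscopy finds relapse, and a relapse found at Month 6 costs no follow-up. If none were found earlier, the arms would have equal follow-up. This stands against any single figure. It does not remove the problem: there is a scheduled endoscopy at Month 1, and symptom-driven endoscopy, withdrawal for lack of efficacy (Protocol 7.5) and withdrawal review for heavy rescue use (Protocol 8.1.1.2) would be expected to take out more placebo subjects in between.

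**The 30-day TEAE window narrows the gap.** It does, but only to 0.61–0.84 even if fully observed, and collection covers only part of it.

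**The tables are descriptive and the bias runs against the test drug.** Both are true. No test of adverse events and no signal threshold is planned, and with equal hazards the distortion makes dexlansoprazole look worse, so it does not conceal harm. It still misstates the comparison.

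**Safety versus placebo is an objective only in the Study Summary.** This stands, so the point does not rest on that sentence. The tables compare arms for Safety Set-M in any case.

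**The listings would allow a correction.** Subject-level exposure and events are listed, and reasons for termination are summarized for the period. An analyst could rebuild the rates, but the plan does not ask for them.

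A reader might go further and infer that relapsed subjects leave at once, that placebo is observed for about half as long, and that the tables would show a false safety signal. The documents do not support this. A ratio near one half needs immediate exit (0.53) or about 80% of failures found at Month 1 (0.55). At a 30% risk, a nominally significant excess is more likely than not only with earlier exit still: 0.69 if all relapses are found at Month 1.

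**Conclusion.** The concern holds in a limited form. The documents establish the exit rule, the large expected difference in failure, the crude percentages and the absence of any exposure adjustment. From these the direction is firm: if some relapse is detected before Month 6, placebo time at risk is expected to be shorter, and the crude dexlansoprazole percentage may be inflated relative to placebo even with identical event hazards.

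The size is not firm. Roughly 4 to 9 points rests on a constant relapse hazard, a 30% event risk over 180 days, a constant event hazard, independent 33% dropout and a 7.5-day tail. SAP 6.0 does not say whether its 33% dropout includes relapse exits. Early clustering of events lowers the excess; a higher background risk or earlier detection raises it. The supportable conclusion is a possible distortion of moderate size in descriptive tables, not a predicted safety signal.

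**What to change.** Keep the crude tables and add the following for Safety Set-M.

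- **SAP 7.7:** summarize exposure and time at risk by arm as well as listing them.
- **SAP 7.11.1:** add exposure-adjusted incidence, as subjects with a first event per 100 patient-months at risk, for all TEAEs, TRAEs and SAEs. Give the between-arm rate difference with a 95% confidence interval for overall TEAEs. State that the comparison with placebo rests on these rates.
- **Person-time:** end each subject's time at the first event or at the end of actual adverse-event observation, consistent with the TEAE window. The 30-day window and the call at 5 to 10 days must be reconciled for this purpose. The imputation in SAP 7.7 of 189 days when the last maintenance dose date is missing should not supply person-time, since it could credit follow-up that did not occur.
- **Hazard check:** these rates assume a roughly constant hazard. Add a cumulative-incidence display of time to first TEAE, or rates by interval. Describe any early-period table as largely, not wholly, before relapse exits: the Month 1 visit has a ±7-day window and symptom-driven endoscopy can come earlier.

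The cost is SAP wording and a few extra tables or figures from data already collected. Trial conduct and the relapse rule are untouched.
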